## 11.2. Efficacy Endpoint Definitions and Analyses

Efficacy analyses will be performed on all subjects who received at least 1 dose of sacituzumab govitecan. For sensitivity purpose, selected efficacy endpoints including ORR, CBR, and PFS will also be analyzed based on the Response Evaluable population, which is defined as all enrolled subjects who have received at least 1 dose of sacituzumab govitecan with a baseline radiologic assessment and at least 1 on-treatment radiological assessment.

Analysis will be conducted separately for each histologic cohort. The primary endpoint, ORR, is defined as the rate of the overall best response, CR or PR, based on the Investigator-assessed tumor response using RECIST 1.1 criteria for each histologic cohort. ORR according to RECIST 1.1 by BICR will be used as a secondary endpoint. The ORR rate will be calculated with a two-sided exact 95% CI using the Clopper-Pearson method.

The secondary endpoint, CBR, is defined as CR + PR + SD for at least 6 months, according to RECIST 1.1 by the Investigator's assessment or BICR. The CBR rate will be calculated with a two-sided exact 95% CI interval using the Clopper-Pearson method.

The secondary endpoint, PFS, is defined as the time from first dose until objective tumor progression or death, whichever comes first. Subjects not experiencing PD or not having died at the time of data cutoff or the database lock will have their event times censored at the last adequate tumor assessment. Tumor progression will be based on Investigator's assessment of tumor response according to RECIST 1.1. A Kaplan-Meier analysis will be performed for the PFS data, and a 95% CI for the median PFS using the Brookmeyer-Crowley CI will be provided. If deemed necessary, PFS analyses according to RECIST 1.1 by BICR-assessed tumor response will also be produced.

The secondary endpoint, DOR, is calculated as the date of the first evaluation showing documented response, either PR or CR, to the date of the first PD or death (or date of last adequate response assessment in case objective PD is censored) according to RECIST 1.1 by the Investigator's assessment. A Kaplan-Meier analysis will be performed for the DOR data, and a 95% Brookmeyer-Crowley CI for the median DOR will be provided. If deemed necessary, DOR analyses according to RECIST 1.1 by BICR-assessed tumor response will also be produced.

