1. INTRODUCTION

This statistical analysis plan (SAP) describes the statistical analysis methods and defines key elements including variable definitions for analysis of data from Study IMMU-132-11 in support of the primary analysis preceding the final analysis. This SAP is based on the study protocol Amendment 5 dated 17 December 2024. Any changes made after the finalization of the SAP will be documented in the CSR.

The purpose of this primary analysis is to summarize the efficacy and safety data for all the participants from non-small cell lung cancer (NSCLC) including adenocarcinoma and squamous cell carcinoma (SCC) cohorts, endometrial carcinoma, head and neck squamous cell carcinoma (HNSCC), and small cell lung cancer (SCLC) cohorts. These cohorts are at the proof of concept (POC) stage of the study. Additional follow-up data from participants in these POC cohorts that are beyond the primary analysis data cutoff date will be summarized in the final analysis that will be prepared once all participants have completed the study.

The biomarker analysis will be described in a separate analysis plan.

Analysis methods specified in this document take precedence over those described in the protocol should there be any difference.

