3.1.2. Full Analysis Set

The Full Analysis Set includes all participants who took at least 1 dose of sacituzumab govitecan. This is the primary analysis set for efficacy analyses.

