Other anti-cancer treatment is initiated	Censored	Date of last adequate tumor assessment before starting other anti-cancer treatment
Other anti-cancer treatment is not initiated	Censored	Date of last adequate tumor assessment

Progression Free Survival (PFS)

PFS will be defined as the time from the date of first dose of study drug to the date of first documentation of disease progression by investigator assessment or BICR based on RECIST v1.1 or death due to any cause, whichever comes first. The censoring rules for PFS are specified in [Table 2](#).

Table 2. Censoring Rules for PFS

Case	Outcome	Date of Event/Censoring
No adequate response assessment after the first dose		
No baseline tumor assessment or alive	Censored	First dose date
Died prior to second scheduled disease assessment without initiation of other anti-cancer therapy	Event	Death date
Died immediately after ≥ 2 consecutive missed assessments or new anti-cancer therapy, if any	Censored	First dose Date
Continued scheduled response assessments until objective PD or death		
PD or death documented after ≤ 1 missed disease assessments, and before other anti-cancer therapy, if any	Event	PD or Death date, whichever occurs first
PD or death immediately after ≥ 2 consecutive missed disease assessments, or after other anti-cancer therapy, if any	Censored	Date of last adequate tumor assessment prior to the earlier date of ≥ 2 consecutive missed disease assessment and other anti-cancer therapy, if any
Continued scheduled response assessments without objective PD or death		
Other anticancer treatment is initiated	Censored	Date of last adequate tumor assessment before starting other anti-cancer treatment
Other anticancer treatment is not initiated	Censored	Date of last adequate response assessment

Overall Survival (OS)

OS will be measured from the date of first dose of study drug to death from any cause. Participants not known to have died are censored on the date they were last known to be alive.

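### SAP Table 2 gives two opposite PFS outcomes for an early death without a baseline tumor assessment, and states no row order

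*SAP*

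**What the plan says.** SAP 6.2.1 measures PFS from first dose to first documented progression "or death due to any cause, whichever comes first". Table 2 then sets the censoring rules. Its first block is headed "No adequate response assessment after the first dose" and has three rows:

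- Row 1: "No baseline tumor assessment or alive". Censored at the first dose date.
- Row 2: "Died prior to second scheduled disease assessment without initiation of other anti-cancer therapy". Event at the death date.
- Row 3: death straight after two or more consecutive missed assessments, or after new anti-cancer therapy. Censored at the first dose date.

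Table 2 does not say which row applies when a participant meets more than one.

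Protocol 11.2 says that PFS "is defined as the time from first dose until objective tumor progression or death, whichever comes first". It describes censoring only for those without either event: "Subjects not experiencing PD or not having died at the time of data cutoff or the database lock will have their event times censored".

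SAP 6.2.2 analyses PFS on the Full Analysis Set, and SAP 3.1.2 asks for no baseline scan: "The Full Analysis Set includes all participants who took at least 1 dose of sacituzumab govitecan". SAP Section 1 settles conflicts with the protocol in the SAP's favour: "Analysis methods specified in this document take precedence over those described in the protocol should there be any difference".

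**The concern.** Row 1 joins its two conditions with *or*. Read literally, a missing baseline assessment is enough for censoring at first dose, whether or not the participant has died. Row 2 makes an early death an event whatever the baseline status. A participant with no baseline assessment who dies early therefore has two prescribed outcomes.

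Two programmers could follow the table faithfully and produce different PFS curves. Under the row 1 reading, the participant leaves the risk set before any event and the death never enters the PFS estimate. From the time of that death onward the curve is higher than it would be if the death counted. The cohorts have only 30 to 40 participants, so one reclassified death is visible in a milestone rate.

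**Working it through.** **Which rows can one participant meet?** Take a treated participant with no adequate post-dose assessment and no new anti-cancer therapy. Protocol Section 9 schedules scans every 6 weeks at first, so the second post-dose scan falls at about week 12.

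| Baseline assessment | Status | Row 1 | Row 2 | Row 3 |
|---|---|---|---|---|
| Yes or no | Alive | Censored, first dose | – | – |
| Yes | Died before second scan | – | Event | – |
| **No** | **Died before second scan** | **Censored, first dose** | **Event** | – |
| No | Died after two or more missed scans | Censored, first dose | – | Censored, first dose |

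Only the third line conflicts. In the fourth line rows 1 and 3 overlap but give the same result.

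**Which outcome fits the definition?** The SAP and protocol definitions both make death an event, and neither makes an exception for a missing baseline scan. Row 2 agrees with them; row 1 does not. The SAP's precedence clause means that the protocol cannot settle the matter, and the clash between two SAP rows remains in any case.

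**Size.** The plan attaches no figure to this rule, so there is nothing to reproduce. Inputs:

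- Cohort sizes n = 30, 35 and 40 (SAP 1.3).
- Earliest PFS milestone: 3 months (SAP 6.2.2).
- Median PFS of 2.3 and 4.0 months. These are assumptions, borrowed from the historical HNSCC and SCLC figures in Protocol 1.2.
- Number of affected deaths per cohort, k. The documents do not give it; 1 to 3 is assumed for illustration.
- Affected deaths placed at 1 month, with no other censoring.

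Let S_c(t) be the Kaplan-Meier curve with the k deaths censored at first dose, and S_e(t) the curve with them counted. Once the deaths have occurred,

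S_e(t) = S_c(t) × (n − k)/n, so S_c(t) − S_e(t) = S_c(t) × k/n.

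The ceiling for k = 1 applies while the curve is still near 1:

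- 1/30 = 3.3 points
- 1/35 = 2.9 points
- 1/40 = 2.5 points

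At 3 months with n = 30:

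| Deaths (k) | Assumed median (months) | Censored | Event | Difference |
|---|---|---|---|---|
| 1 | 2.3 | 0.414 | 0.400 | 0.414/30 = 0.0138, or 1.4 points |
| 1 | 4.0 | 0.586 | 0.567 | 0.586/30 = 0.0195, or about 2.0 points (1.9 from the rounded rates) |
| 3 | 2.3 | 0.407 | 0.367 | 4.0 points |
| 3 | 4.0 | 0.593 | 0.533 | 6.0 points |

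Under an exponential curve, the median with the deaths counted, relative to the median with them censored, is ln(2(1 − k/n))/ln 2:

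- k = 1, n = 30: 0.951, about 5% shorter.
- k = 1, n = 40: 0.963, about 4% shorter.
- k = 3, n = 30: 0.848, about 15% shorter.

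If k = 0, every difference is zero.

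**The case against.** **The group should be close to empty.** This stands. Protocol 4.2 makes CT or MRI a screening evaluation, and criterion 8 in Protocol 6.2 requires measurable disease. Protocol Section 4 forbids eligibility waivers, and Section 5 bars dosing until the sponsor or its representative has approved the eligibility packet. A reader might take the Efficacy Evaluable Analysis Set (SAP 3.1.3) or the eligibility-deviation summary (SAP Section 4) as a sign that missing baseline scans are expected. They do not show that. The first turns on measurable disease and a post-baseline assessment, and a participant with only non-measurable disease still has a baseline assessment. The second is generic. PFS by central review also needs a usable baseline scan to reach the central reader, which site eligibility does not guarantee, but that is inference and no count is given.

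**Row 1 does not reach everyone without a baseline assessment.** This also stands. The block heading confines it to participants with no adequate assessment after first dose, so a reading that it censors any participant lacking a baseline scan goes too far.

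**Table 2 censors other deaths too.** It does so after missed assessments or new therapy, so departing from the bare definition is not peculiar to row 1. First-dose censoring without a baseline could be deliberate, since RECIST change cannot be judged without one. That weakens the argument from the definition alone. It does not remove the overlap: if row 1 is meant to prevail, the table has to say so, because row 2 says the opposite.

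**Little depends on it.** PFS is a descriptive secondary endpoint, and the proof-of-concept stage has no hypothesis (SAP 6.1.2). ORR is unaffected. A reader might infer that a death vanishes from the trial. It does not: it still counts in OS (SAP 6.2.1) and in the death summary (SAP 7.1.6.2).

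**Conclusion.** The point holds as a narrow internal contradiction of low severity. Within the block for no adequate post-dose assessment, rows 1 and 2 assign opposite outcomes to the same participant, with no order stated, and the row 1 outcome departs from both PFS definitions. From the death onward, the row 1 reading can only raise the PFS curve.

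The size is S_c(t)/n per affected death. The 3.3, 2.9 and 2.5 points are ceilings and should not be read as the effect on a reported milestone. At 3 months with n = 30, the effect is about 1.4 to 2.0 points for one death. That rests on the assumed medians of 2.3 to 4.0 months, one assumed case and no other censoring. The documents do not say that any such participant exists; if none does, the effect is nil. They give no ground for reading this as a threat to the primary endpoint or to OS.

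**What to change.** Reword the two rows so that they exclude each other and match the PFS definition:

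- Row 1: *Alive, with no baseline or no adequate post-baseline assessment: censored at first dose date.*
- Row 2: *Died before the second scheduled assessment without other anti-cancer therapy, with or without a baseline assessment: event at death date.*

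Row 3 can stay as it is. If censoring at first dose is intended for deaths without a baseline assessment, state instead that row 1 takes priority over row 2, and declare it as a departure from the PFS definition.

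The cost is the wording of two table rows, with no new data and no design change. SAP Section 1 already provides for changes after finalization to be documented in the CSR. PFS would either be unchanged or become marginally less favourable.

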6.2.2. Analysis Methods for Secondary Efficacy Endpoints

Clinical Benefit Rate (CBR) and Disease Control Rate (DCR)

CBR and DCR will be summarized for the Full Analysis Set along with the number and percent of participants in each response category. 95% confidence intervals of CBR and DCR will be calculated using the Clopper Pearson method [{Clopper 1934}](#). An additional sensitivity analysis of CBR and DCR may be performed based on the Efficacy Evaluable Analysis Set.

Duration of Response (DOR)

The analysis of duration of response (DOR) will be performed using the Kaplan-Meier method for the responding participants in the Full Analysis Set. Median, Q1, and Q3 of the DOR will be provided along with the corresponding 95% CI for each cohort. Kaplan-Meier curves will be provided by cohort.

The follow-up time for DOR, defined as the time from the first documentation of response according to RECIST v1.1. to the date of death or the last known alive date if participants are not dead, will be summarized descriptively.

Progression Free Survival (PFS)

A Kaplan-Meier analysis will be performed for the PFS data using the Full Analysis Set. Median PFS will be derived and 95% confidence will be calculated based on Brookmeyer and Crowley method [{Brookmeyer 1982}](#). The milestone PFS rate at 3 months, 6 months, 12 months, 18 months will be derived from the KM curve.

Overall Survival (OS)

A Kaplan-Meier analysis will be performed for the OS data using the Full Analysis Set. Median OS will be derived, and 95% confidence will be calculated based on Brookmeyer and Crowley method [{Brookmeyer 1982}](#). The milestone OS rate at 6 months, 12 months, and 24 months will be derived from the KM curve.

The follow-up time for OS, defined as the time from the date of first dose of study drug to the date of death or the last known alive date if participants are not dead, will be summarized descriptively.

7. SAFETY ANALYSES

7.1. Adverse Events and Deaths

7.1.1. Adverse Events Dictionary

Clinical and laboratory adverse events (AEs) will be coded using the Medical Dictionary for Regulatory Activities (MedDRA). System organ class (SOC), high level group term (HLGT), high level term (HLT), preferred term (PT), and lower level term (LLT) will be provided in the AE dataset.

7.1.2. Adverse Events Severity

Adverse events are graded by the investigator as Grade 1, 2, 3, 4, or 5 according to NCI CTCAE Version 5.0. The severity grade of events for which the investigator did not record severity will be categorized as “missing” for tabular summaries and data listings. The missing category will be listed last in summary presentation.

7.1.3. Relationship of Adverse Events to Study Drug

Related AEs are those for which the investigator selected “Related” or “Possibly Related” on the AE CRF to the question of “Related to Study Treatment.” Relatedness will always default to the investigator’s choice, not that of the medical monitor. Events for which the investigator did not record relationship to study drug will be considered related to study drug for summary purposes. However, by-participant data listings will show the relationship as missing.

7.1.4. Serious Adverse Events

Serious adverse events (SAEs) will be identified and captured as SAEs if the AEs met the definitions of SAEs that were specified in the study protocol. SAEs captured and stored in the clinical database will be reconciled with the SAE database from the Gilead Patient Safety Department before data finalization.

7.1.5. Treatment-Emergent Adverse Events

7.1.5.1. Definition of Treatment-Emergent Adverse Events

Treatment-emergent adverse events (TEAEs) are defined as any AEs with an onset date on or after the study drug start date and no later than 30 days after last dose of study drug or the day before initiation of subsequent anticancer therapy, whichever comes first.

7.1.6. Summaries of Adverse Events and Deaths

Treatment-emergent AEs will be summarized based on the Safety Analysis Set.

7.1.6.1. Summaries of AE Incidence

Treatment-emergent AEs, SAEs, grade 3 or worse TEAEs, treatment-related TEAEs, TEAEs leading to study drug discontinuation, TEAEs leading to study drug interruption, TEAEs leading to dose reduction, TEAEs leading to death, protocol - defined AEs of special interest and other safety observations will be summarized based on the Safety Analysis Set. SAEs occurring beyond reporting period may be listed.

A brief, high-level summary of the number and percent of participants who experienced at least 1 TEAE in the categories described below will be provided by cohort. All deaths observed in the study will also be included in this summary.

The number and percent of participants who experienced at least 1 TEAE will be provided and summarized by SOC, PT and cohort:

- TEAEs
- TEAEs with Grade 3 or higher
- TE treatment-related AEs
- TE treatment-related AEs with Grade 3 or higher
- TE SAEs
- TE treatment-related SAEs
- TEAEs leading to discontinuation of study drug
- TEAEs leading to death
- TE Treatment-related AEs leading to death
- TEAEs leading to interruption of study drug
- TEAEs leading to dose reduction

For AE categories described below, summaries will be provided by SOC, PT, maximum severity and cohort:

- TEAEs
- TE Treatment-related AEs

- TE Treatment-related AEs with Grade 3 or higher

For AE categories described below, summaries will be provided by PT and cohort:

- TEAEs reported by $\geq 10\%$ participants
- TE treatment-related AEs reported by $\geq 5\%$ participants
- TEAEs with CTCAE Grade 3 or higher reported by $\geq 2\%$ participants
- TE SAE reported by $\geq 2\%$ participants
- TEAEs leading to dose reduction
- TEAEs leading to interruption of study drug
- TEAEs leading to discontinuation of study drug

Multiple events will be counted only once per participant in each summary. Adverse events will be summarized and listed first in alphabetic order of SOC, and then by PT in descending order of total frequency within each SOC. For summaries by severity grade, the worst severity will be used for those AEs that occurred more than once in an individual participant during the study.

In addition to the above summary tables, all TEAEs, TE SAEs, TE treatment-related AEs, and TE treatment-related SAEs will be summarized by PT only, in descending order of total frequency.

In addition, data listings will be provided for the following:

- AEs, indicating whether the event is treatment emergent
- SAEs
- Deaths
- AEs with CTCAE Grade 3 or higher
- AEs leading to discontinuation of any study drug
- AEs leading to dose interruption of study drug
- AEs leading to death

7.1.6.2. Summary of Death

A summary (number and percent of participants) of deaths will be provided by cohort. Summary will include the following categories:

- All deaths
- Deaths within 30 days of the last dosing of study drug
- Deaths beyond 30 days of the last dosing of study drug

The attribution of death, if available, will also be summarized.

7.1.7. Additional Analysis of Adverse Events

7.1.7.1. Subgroup Analysis of TEAE

The subgroup analysis for the TEAE by age (< 65, ≥ 65 years) will be performed by SOC, PT, and age group for the Safety Analysis Set.

7.1.7.2. Treatment-emergent Adverse Events of Special Interest (TEAESI)

Definitions of treatment-emergent adverse events of special interest (TEAESI) for SG are provided in [Table 3](#).

Table 3. Definitions of Adverse Events of Special Interest

AESI	Definition
Serious infections secondary to neutropenia	Preferred terms under SOC: Infections and Infestations ^a (serious infections occurring after AE of neutropenia of any grade)
Severe diarrhea	Preferred term: diarrhea (Grade 3 or higher)
Hypersensitivity ^b	Preferred terms under: Hypersensitivity SMQ (narrow) and Anaphylactic Reaction SMQ (broad and narrow) ^c
Neutropenia ^d	Preferred terms: neutropenia, neutrophil count decreased, febrile neutropenia

AE = adverse event; AESI = adverse event of special interest; MedDRA = Medical Dictionary for Regulatory Activities; SMQ = Standardized MedDRA Query; SOC = system organ class

All definitions are based on MedDRA Version 26.1 or higher.

a Serious AEs from the Infections and Infestations SOC that occurred within 11 days of neutropenia, febrile neutropenia, or neutrophil count decreased.

b For the category of hypersensitivity, only events with onset dates on the day of or 1 day after study drug administration are included.

c Anaphylactic Reaction SMQ (broad and narrow) is an algorithmic SMQ.

d Grouped AE terms.

A high-level summary of the number and percent of participants who experienced at least 1 TEAESI in the categories described below will be provided by cohort. The following summaries will be provided for TEAESIs by Category, PT and cohort:

- TEAESI
- TEAESIs with Grade 3 or higher
- Treatment-related TEAESIs
- TE Serious AESI
- TEAESIs leading to interruption of study drug
- TEAESIs leading to discontinuation of study drug
- TEAESIs leading to dose reduction of study drug
- TEAESIs leading to death

A corresponding data listing of TEAESIs will be provided.

7.2. Laboratory Evaluations

Selected laboratory test data will be summarized. Local laboratory results will be standardized using the International System SI unit.

Graded laboratory abnormalities will be defined using the grading scheme. The worst toxicity grade during the study will be tabulated.

The number and percent of participants with treatment-emergent laboratory abnormalities will be summarized by cohort. A treatment-emergent laboratory abnormality will be defined as any value that increases at least 1 toxicity grade from baseline during the treatment emergent period.

A by-participant listing for laboratory test results will be provided by participant ID number and visit in chronological order for hematology, serum chemistry, and urinalysis separately. Values falling outside of the relevant reference range and/or having a severity grade of 1 or higher on the CTCAE severity grade will be flagged in the data listings, as appropriate.

Laboratory abnormalities that occur before the first dose of study drug or after the participant has been discontinued from treatment for ≥ 30 days will be included in a data listing.

